**Figure 2      Management of Hypertension**

BP = blood pressure, HTN = hypertension, Tx = treatment.

#### 9.4.1.1.3 MANAGEMENT OF POSTERIOR REVERSIBLE ENCEPHALOPATHY SYNDROME/REVERSIBLE POSTERIOR LEUKOENCEPHALOPATHY SYNDROME

Posterior Reversible encephalopathy Syndrome (PRES)/Reversible Posterior Leukoencephalopathy Syndrome (RPLS) is a neurological disorder that can present with headache, seizure, lethargy, confusion, altered mental function, blindness, and other visual or neurological disturbances. Mild to severe hypertension may be present. An MRI is necessary to confirm the diagnosis of PRES/RPLS. Appropriate measures should be taken to control BP (see [Section 9.4.1.1.1](#) and [9.4.1.1.2](#)), and neurologic consultation is advised. In subjects with signs or symptoms of PRES/RPLS, dose modification guidelines as per [Table 1](#) should be followed.

#### 9.4.1.1.4 MANAGEMENT OF PROTEINURIA

Regular assessment for proteinuria should be conducted as detailed in the Schedule of Assessments ([Table 5](#) and [Table 6](#)). Guidelines for assessment and management of proteinuria are summarized as follows:

##### Grading of Proteinuria

- Grading according to CTCAE 5.0 ([Cancer Therapy Evaluation Program, 2017](#)) will be based on the protein-creatinine ratio or 24-hour urinary protein result, if available. For subjects  $\geq 18$  years of age, if the subject has 4+ proteinuria by dipstick, a 24-hour urinary protein result is required to confirm Grade 3 proteinuria.

##### Management of Proteinuria

- Management of lenvatinib administration will be based on the grade of proteinuria according to [Table 1](#).
- In the event of nephrotic syndrome, lenvatinib must be discontinued.

##### Detection and Confirmation

- Perform urine dipstick testing per the Schedule of Assessments ([Table 5](#) and [Table 6](#))
- For subjects  $\geq 18$  years of age, a 24-hour urine collection initiated as soon as possible and at least within 72 hours (or an immediate spot urine protein-to-creatinine ratio [UPCR] test) AND for subjects  $< 18$  years of age, an immediate spot UPCR test, and if possible, a 24-hour urine collection (initiated as soon as possible and at least within 72 hours) is required in the following situations:
  - The first (initial) occurrence of  $\geq 2+$  proteinuria on urine dipstick while on lenvatinib
  - A subsequent increase in severity of urine dipstick proteinuria occurring on the same lenvatinib dose level
  - When there has been a lenvatinib dose reduction and at the new dose level the urine protein dipstick result is  $\geq 2+$
- For subjects  $\geq 18$  years of age, a 24-hour urine collection (initiated as soon as possible and at least within 72 hours) to verify the grade of proteinuria is required when UPCR is  $\geq 2.4$ .

## Monitoring

- Urine dipstick testing for subjects with proteinuria  $\geq 2+$  should be performed on Day 15 (or more frequently as clinically indicated) until the results have been 1+ or negative for 2 consecutive treatment cycles.
- Proteinuria monitoring can be performed at the local laboratory or investigator site, but must be managed by the site physician.

### 9.4.1.1.5 MANAGEMENT OF HEPATOTOXICITY

Regular monitoring of liver function tests (ALT, AST, bilirubin levels) should be conducted as detailed in the Schedule of Assessments ([Table 5](#) and [Table 6](#)) and as clinically indicated. If signs/symptoms indicating liver injury occur, instructions contained in the table for dose reduction and interruptions of the protocol should be followed (see [Table 1](#)). Appropriate supportive care should be provided together with close monitoring. If hepatic (any grade per CTCAE v5) failure occurs the study drug must be discontinued.

### 9.4.1.1.6 MANAGEMENT OF THROMBOEMBOLIC EVENTS

Subjects should be advised to pay attention to symptoms suggestive of venous thromboembolic events which include acute onset of shortness of breath, dyspnea, chest pain, cough, hemoptysis, tachypnea, tachycardia, cyanosis, deep vein thrombosis signs including lower-extremity swelling, redness and warmth to touch or tenderness. In case any of these symptoms appear, subjects should be instructed to report such symptoms promptly to the treating physician. If a thromboembolic event is confirmed, instructions contained in the table for dose reduction and interruptions of the protocol should be followed (see [Table 1](#)). Appropriate supportive care should be provided together with close monitoring. If a subject experiences a Grade 3 or a life-threatening (Grade 4) thromboembolic reaction, including pulmonary embolism, study drug must be discontinued.

Arterial thromboembolic events (eg, new onset, worsening, or unstable angina, myocardial infarction, transient ischemic attack, and cerebrovascular accident) of any grade require study drug discontinuation.

### 9.4.1.1.7 MANAGEMENT OF HYPOCALCEMIA

Serum calcium should be monitored monthly per the Schedule of Assessments ([Table 5](#) and [Table 6](#)). Corrected serum calcium should be used to assess the grade of hypocalcemia per CTCAE v5.0, using the following formula:

$$\text{Corrected calcium} = ([4 - \text{serum albumin in g/dL}] \times 0.8 + \text{serum calcium})$$

The formula is not applicable when serum albumin concentration is normal ( $>4$  g/dL); in such situations, the total (uncorrected) serum calcium should be used instead.

Hypocalcemia should be treated per institutional guidelines (eg, using appropriate calcium, magnesium, and Vitamin D supplementation) until resolution.

#### 9.4.1.1.8 MANAGEMENT OF GASTROINTESTINAL SYMPTOMS AND ACUTE ABDOMINAL PAIN

Initial management of acute abdominal pain in these study subjects should be focused on treating the underlying cause where possible, ensuring appropriate hydration/rehydration, and symptomatic pain improvement consistent with subject's age and in accordance to local and institutional standards of care. Appropriate supportive care should be provided together with close monitoring.

For adverse events of abdominal pain believed related to lenvatinib or more specific adverse events believed related to lenvatinib that result in the symptom of abdominal pain, follow instructions contained in [Table 1](#) regarding study treatment dose reduction and interruption. For Grade 4 adverse events that result in abdominal pain, study drug must be discontinued.

Gastrointestinal symptoms including diarrhea should be managed by providing symptomatic treatment. If the symptoms persist (eg, diarrhea for more than 10 days), dose modification guidelines should be followed as per [Table 1](#). Gastrointestinal symptoms should be monitored closely and evaluated using CT, contrast-enhanced MRI, ultrasound, or other diagnostic imaging if clinically indicated, at the investigator's discretion.

#### 9.4.1.1.9 MANAGEMENT OF HEMORRHAGE

Dose modification guidelines as per [Table 1](#) for lenvatinib related adverse events should be followed for the management of hemorrhage. Either resume lenvatinib at a reduced dose or discontinue lenvatinib, depending on the severity and persistence of hemorrhage.

#### 9.4.1.1.10 MANAGEMENT OF FISTULA FORMATION AND GASTROINTESTINAL PERFORATION

Lenvatinib should be discontinued in any participants who develop grade  $\geq 4$  fistula (gastrointestinal or non-gastrointestinal), or gastrointestinal perforation of any grade.

#### 9.4.1.1.11 MANAGEMENT GUIDELINES FOR QT PROLONGATION

Lenvatinib should be withheld in the event of development of QT interval prolongation greater than 500 msec. Lenvatinib should be resumed at a reduced dose when QTc prolongation is resolved to  $< 480$  msec or baseline. Monitor potassium, calcium and magnesium, and replenish as appropriate.

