### 9.3.2 Exclusion Criteria

Subjects who meet any of the following criteria will be excluded from this study:

1. Any active infection or infectious illness unless fully recovered prior to Cycle 1 Day 1 (ie, no longer requiring systemic treatment).
2. Subjects with central nervous system metastases are not eligible, unless they have completed local therapy (eg, whole brain radiation therapy, surgery or radiosurgery) and have discontinued the use of corticosteroids for this indication for at least 2 weeks before Cycle 1 Day 1.
3. Active second malignancy within 2 years prior to enrollment ([in addition to osteosarcoma], but not including definitively treated superficial melanoma, carcinoma-in-situ, basal or squamous cell carcinoma of the skin).
4. Any medical or other condition that in the opinion of the investigator(s) would preclude the subject's participation in a clinical study.
5. Has had major surgery within 3 weeks prior to Cycle 1 Day 1.
  - Note: Adequate wound healing after major surgery must be assessed clinically, independent of time elapsed for eligibility.
6. Known hypersensitivity to any component(s) of the study drugs (lenvatinib, ifosfamide, and etoposide, or their ingredients).
7. Currently receiving any investigational drug or device in another clinical study or within 28 days prior to Cycle 1 Day 1.
8. A clinically significant ECG abnormality, including a marked baseline prolonged QT or QTc interval (eg, a repeated demonstration of a QTc interval >480 msec).
9. Has clinically significant cardiovascular disease within 6 months from first dose of study intervention, including New York Heart Association Class III or IV congestive heart failure, unstable angina, myocardial infarction, cerebral vascular accident, or cardiac arrhythmia associated with hemodynamic instability. **Note:** Medically controlled arrhythmia would be permitted.
10. Gastrointestinal malabsorption, gastrointestinal anastomosis, or any other condition that in the opinion of the investigator might affect the absorption of lenvatinib.
11. Pre-existing Grade  $\geq 3$  gastrointestinal or non-gastrointestinal fistula.
12. Gastrointestinal bleeding or active hemoptysis (bright red blood of at least  $\frac{1}{2}$  teaspoon) within 3 weeks prior to Cycle 1 Day 1.

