#### 9.4.1.1 Lenvatinib Dose Reduction and Interruption Instructions

Adverse events will be graded using CTCAE version 5.0.

Dose reduction and interruptions for subjects who experience lenvatinib related toxicity will be managed as described in [Table 1](#).

The starting dose of lenvatinib is 14 mg/m^2. Dose reductions occur in succession based on the previous dose level. Each dose level reduction is a 20% reduction from the previous dose.

Once the study drug dose level has been reduced, it may not be increased at a later date, unless the dose was mistakenly decreased; in this situation, the sponsor's approval is required to increase the dose.

Refer to the subsections below for management of hypertension, posterior reversible encephalopathy syndrome/reversible posterior leukoencephalopathy syndrome (PRES/RPLS), proteinuria, hepatotoxicity, thromboembolic events, hypocalcemia, gastrointestinal symptoms and acute abdominal pain, and hemorrhage, as appropriate, before consulting the dose modification table below.

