**Table 1 Criteria for Temporary Discontinuation of Study Drug, Dose Reduction, and Resumption of Treatment**

Dose Modification Guidelines for Lenvatinib Related Toxicity		
Treatment-Related Toxicitya,b	Management	Dose Adjustment
Grade 1 or Tolerable Grade 2		
	Continue treatment	No change
Intolerable Grade 2c,d or Grade 3e		
First occurrence	Interrupt lenvatinib until resolved to Grade 0-1, or tolerable Grade 2	11.2 mg/m  (or 20% reduction of the starting dose) orally QD (one-level reduction)
Second occurrence (same toxicity or new toxicity)	Interrupt lenvatinib until resolved to Grade 0-1, or tolerable Grade 2	9.0 mg/m  (or 20% reduction of the previous dose) orally QD (one-level reduction)
Third occurrence (same toxicity or new toxicity)	Interrupt lenvatinib until resolved to Grade 0-1, or tolerable Grade 2	7.2 mg/m  (or 20% reduction of the previous dose) orally QD (one-level reduction)
Fourth occurrence (same toxicity or new toxicity)	Interrupt lenvatinib	Discuss with sponsor
Grade 4f: Discontinue Study Treatment		

Note: For grading see [CTCAE version 5.0](#). Collect all CTC grades of adverse events, decreasing and increasing grade.

BMI = body mass index, CTCAE = Common Terminology Criteria for Adverse Events

- a: An interruption of study treatment for more than 28 days will require sponsor's approval before treatment can be resumed.
- b: Initiate optimal medical management for nausea, vomiting, hypertension, hypothyroidism, and/or diarrhea prior to any study treatment interruption or dose reduction.
- c: Applicable only to Grade 2 toxicities judged by the subject and/or physician to be intolerable.

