Abnormal ECG (QTcF) results, if not otherwise considered part of a clinical symptom that is being reported as an AE, should be considered an AE if the QTcF interval is more than 450 ms and there is an increase of more than 60 ms from baseline. Any ECG abnormality that the investigator considers as an AE should be reported as such.

All AEs must be followed for 30 days after the subject's last study drug dose, or until resolution, whichever comes first. Subjects with onset of an AE or deterioration of a preexisting AE during the AE collection period will be followed until resolution to baseline, start of a new anticancer treatment, or death. All SAEs must be followed to resolution or, if resolution is unlikely, to stabilization.

**Every effort must be made by the investigator to categorize each AE according to its severity and its relationship to the study treatment.**

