#### 9.5.1.4.6 ELECTROCARDIOGRAMS

Electrocardiograms will be obtained as designated in the Schedule of Assessments ([Table 5](#) and [Table 6](#)). Complete, standardized, 12-lead ECG recordings that permit all 12 leads to be displayed on a single page with an accompanying lead II rhythm strip below the customary 3×4 lead format are to be used. In addition to a rhythm strip, a minimum of 3 full complexes should be recorded from each lead simultaneously. If possible, subjects must be in the recumbent position for a period of 5 minutes prior to the ECG.

QTc prolongation has been seen in some lenvatinib studies. Monitor ECGs every cycle (as specified in the Schedule of Assessments) in participants with congenital long QT syndrome, congestive heart failure, bradyarrhythmias, or those who are taking drugs known to prolong the QT interval, including Class Ia and III antiarrhythmics. Drugs known to prolong the QTc interval (including Class Ia and III antiarrhythmics) must be used cautiously. Please refer to the lenvatinib IB or lenvatinib prescribing information.

An ECG abnormality may meet the criteria of an AE as described in this protocol (see [Section 9.5.1.4.1](#)) and the CRF Completion Guidelines. In these instances, the AE corresponding to the ECG abnormality will be recorded on the Adverse Events CRF.

For ECG abnormalities meeting criteria of an SAE (see Serious Adverse Events and Other Events of Interest), the study site must fax the SAE report including the ECG report to the number indicated in the Investigator File using the SAE reporting form (see [Section 9.5.4.1](#)).

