#### 9.7.1.8.5 ELECTROCARDIOGRAMS

Descriptive statistics for electrocardiogram parameters (HR, PR, QRS, QT, QTcB, QTcF and RR) and changes from Baseline will be presented by visit. Electrocardiogram (ECG) findings will be summarized. A shift table of worst postbaseline values from Baseline for ECG findings will be provided.

QTc Bazett and QTc Fridericia will be summarized. QTc Bazett and QTc Fridericia will be categorized as both maximum increases from Baseline and maximum postbaseline values.

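### The QT dose rule in Protocol Section 9.4.1.1.11 holds lenvatinib on uncorrected QT but restarts it on QTc, with no correction formula named

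*Protocol*

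**What the plan says.** Section 9.4.1.1.11, added in Amendment 02, gives the hold in one sentence and the restart in the next. The hold reads "Lenvatinib should be withheld in the event of development of QT interval prolongation greater than 500 msec". The restart sentence begins "Lenvatinib should be resumed at a reduced dose when QTc prolongation is resolved to"; its limit is under 480 msec, with return to baseline as the alternative. No correction formula appears in the section. The abbreviation list in Section 4 defines QTc as QT corrected for heart rate.

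Other places that bear on the rule:

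- **Section 9.3.2, exclusion 8** gives as its example "a repeated demonstration of a QTc interval >480 msec". It names no formula.
- **Section 9.5.1.4.1** sets its ECG reporting criterion on the Fridericia interval: "should be considered an AE if the QTcF interval is more than 450 ms and there is an increase of more than 60 ms". The rise is measured against baseline. This is the only place where a formula is tied to a clinical action.
- **Section 9.7.1.8.5** says "QTc Bazett and QTc Fridericia will be summarized". It lists QT, QTcB and QTcF as separate parameters and ranks neither formula.
- **Section 9.4.1.1** says of lenvatinib dosing: "Once the study drug dose level has been reduced, it may not be increased at a later date". The only exception is a mistaken reduction.
- **Section 9.5.1.4.6** notes that "QTc prolongation has been seen in some lenvatinib studies". It asks for an ECG every cycle in certain groups, including subjects with bradyarrhythmias.

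**The concern.** A hold limit and its restart limit should refer to the same measurement, and here they do not. Nothing in the protocol says that QT in the hold sentence means QTc.

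An investigator who follows the hold sentence literally applies a threshold whose corrected value rises with heart rate, so above 60 bpm the drug is stopped later than a QTc limit of 500 msec would require. At slow rates the rule can contradict itself, because a tracing may be long enough to stop the drug while its QTc is already short enough to restart it.

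The decision has lasting effects. A restart is at a lower dose, and that dose cannot be raised again. Subjects in Arm A and Arm B subjects who cross over are exposed to the rule, at about 80 sites (Section 6), with no common instruction on which QTc to read.

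**Working it through.** **Inputs.** The hold limit (QT above 500 msec) and the restart limit (QTc below 480 msec or baseline) come from Section 9.4.1.1.11. The two formulas, Fridericia and Bazett, are those named in Section 9.7.1.8.5. The protocol gives no heart rates, so 50 to 100 bpm is an assumed range for illustration. The protocol also states no derived figure to reproduce on this point.

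**Formulas.** With RR = 60/HR in seconds:

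- QTcF = QT / RR^(1/3)
- QTcB = QT / RR^(1/2)

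**Step 1: what the literal hold limit means on the corrected scale**

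| HR (bpm) | RR (s) | QTcF at QT 500 (msec) | QTcB at QT 500 (msec) | QT at QTcF 500 (msec) |
|---|---|---|---|---|
| 50 | 1.200 | 471 | 456 | 531 |
| 60 | 1.000 | 500 | 500 | 500 |
| 70 | 0.857 | 526 | 540 | 475 |
| 80 | 0.750 | 550 | 577 | 454 |
| 100 | 0.600 | 593 | 645 | 422 |

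At 100 bpm a subject whose QTcF has just passed 500 msec has a QT of about 422 msec, which is 78 msec short of the literal hold limit (500 − 422). This section's hold would not apply until QTcF reached about 593 msec.

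**Step 2: when one tracing meets both limits.** A QT of 500 msec has a QTc of 480 msec when RR^(1/3) = 500/480 (Fridericia) or RR^(1/2) = 500/480 (Bazett). Solving for heart rate:

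- Fridericia: HR = 60 × (480/500)^3 = 53.1 bpm
- Bazett: HR = 60 × (480/500)^2 = 55.3 bpm

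Below these rates, a QT just above 500 msec already satisfies the restart limit. The band is narrow. At 50 bpm the QT that gives QTcF 480 is 480 × 1.2^(1/3) = 510 msec, so the overlap runs from 500 to 510 msec.

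**Step 3: QTc read into both sentences.** The mismatch in Steps 1 and 2 disappears, but the formula still decides the restart. At 80 bpm:

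- The 480 msec limit corresponds to a QT of 480 × 0.75^(1/3) = 436 msec (Fridericia) or 480 × 0.75^(1/2) = 416 msec (Bazett).
- A QT of 425 msec lies between them: QTcF = 425 / 0.75^(1/3) = 468 msec (restart) and QTcB = 425 / 0.75^(1/2) = 491 msec (no restart).

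The formulas therefore disagree for QT from 416 to 436 msec at 80 bpm. At 100 bpm the corresponding range is 372 to 405 msec.

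**The case against.** The best counter-argument is that the paragraph explains itself. The restart sentence speaks of QTc prolongation having resolved, and only the event that caused the hold can resolve, so the hold must have been for QTc. Section 9.5.1.4.6 supports this: it describes the same antiarrhythmic classes as prolonging QT in one sentence and QTc in the next. The other numeric ECG limits in the protocol are all on a corrected interval. On that reading, Steps 1 and 2 of the working fall away and only the unnamed formula remains. This probably is what the authors meant. It is still an inference, and a dose rule for a cardiac risk should not depend on one.

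There is also a backstop. A QTcF rise that meets Section 9.5.1.4.1 is an adverse event and is graded by CTCAE. For a treatment-related Grade 3 or intolerable Grade 2 event, Table 1 says "Interrupt lenvatinib until resolved to Grade 0-1, or tolerable Grade 2". This may stop the drug before a QT of 500 msec is reached, so the literal figures should not be taken as the expected clinical outcome. How far it covers the gap cannot be checked, because the CTCAE cut-offs are not in the protocol. Section 9.4.1.1 lists the toxicity subsections to consult before Table 1, and QT prolongation is not among them, so it is unclear which rule governs.

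The lenvatinib label or Investigator's Brochure may clarify the measure. Neither is available here, and the dosing text should be clear without them.

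**Conclusion.** The point holds, and the section is wrong as written. The hold is on QT, the restart is on QTc, the protocol itself defines these as different quantities, and no formula is named for the dose rule.

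Followed literally, the hold acts at QTcF 526, 550 and 593 msec at 70, 80 and 100 bpm, and the two limits overlap narrowly below 53.1 bpm (Fridericia) or 55.3 bpm (Bazett). With QTc read into both sentences, the remaining effect is a formula-dependent restart, over a QT range of about 20 msec at 80 bpm (436 − 416).

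These sizes rest on assumed heart rates, and at 60 bpm there is no effect. The wording is probably a drafting slip, and Table 1 limits the consequence. The primary PFS analysis is not materially affected. The sponsor should correct it because it is a safety threshold and the correction is trivial.

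**What to change.** Reword Section 9.4.1.1.11 so that both limits use one named interval: withhold lenvatinib when QTcF exceeds 500 msec, and resume at a reduced dose when QTcF is below 480 msec or has returned to baseline. Fridericia is the natural choice because Section 9.5.1.4.1 already uses it for adverse-event reporting.

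The cost is a few words in one paragraph. Sections 9.5.1.4.1 and 9.7.1.8.5 already require QTcF, so no new procedure or data item should be needed.

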#### 9.4.1.2 Management of Ifosfamide-Etoposide Associated Toxicity

Blood counts should be closely monitored during and prior to the next cycle of chemotherapy. Chemotherapy-associated myelosuppression should be managed by granulocyte-colony stimulating factor (G-CSF). It is recommended that pegylated G-CSF or G-CSF be administered at least 24 to 72 hours after completion of ifosfamide-etoposide chemotherapy; use of G-CSF is recommended until white blood cell (WBC) counts are  $\geq 1 \times 10^9/L$ . Guidelines for dose modification for ifosfamide and etoposide associated toxicities are provided in the [Table 2](#) below.

Details of ifosfamide and etoposide dose interruption and reduction as well as management of toxicity can be found in the Summary of Product Characteristics (SmPC), and may be followed as per local and institutional guidelines. The SmPC will be provided to the study sites in the Investigator and Pharmacy files in the relevant local language. For additional information investigators may refer to the SmPC or Euramos-1 protocol (ISRCTN67613327 EudraCT no. 2004-000242-20).

